#### 6.3 Patient data

#### Patient disposition

- Patients enrolled / in FAS (yes, no)
- Patients fulfilling all selection criteria (yes, no)
  - o If no: List of patients violating any selection criteria

#### **Demographics**

- · Age calculated as year of visit minus year of birth
- Gender
- Race
- Education
- Residence of the patient

#### Parkinson's disease history

- Time since PD diagnosis calculated as year of visit minus year of PD diagnosis + 1
- Age at PD diagnosis calculated as year of PD diagnosis minus year of birth
- PD motor phenotype
- Time from PD diagnosis to motor fluctuation onset calculated as year of motor fluctuation onset minus year of PD diagnosis +1
- Time from PD diagnosis to start of LCIG calculated as year of first start date of LCIG initiation minus year of PD diagnosis +1
- Morning akinesia (yes, no)
  - If yes: time from PD diagnosis to onset of morning akinesia calculated as year of onset of morning akinesia minus year of PD diagnosis +1
- Wearing off (yes, no)
  - If yes: time from PD diagnosis to onset of wearing off calculated as year of onset of wearing off minus year of PD diagnosis +1
- Dyskinesia present (yes, no)
  - If yes: time from PD diagnosis to onset of dyskinesia calculated as minus year of onset of dyskinesia minus year of PD diagnosis +1

#### Clinical PD status immediately prior to / at LCIG initiation

- Duration of 'Off' state time during a 24h period (hours)
- Duration of dyskinesia during a 24h period (hours)
- Severity of dyskinesia
- Reason for LCIG start (multiple answers)
- Conduction of Nasojejunal test phase (yes, no)
  - If yes: reason (multiple answers)
  - If no: reason (multiple answers)
- Duration of titration calculated as date of titration finalization minus date of titration initiation +1
- Duration of LCIG treatment calculated as visit date minus date of LCIG initiation start +1
- Hospitalization for titration and PEG-J placement (yes, no)
- Hospitalization for PEG-J placement (yes, no)

#### Motor symptoms

Separately for 'immediately prior to LCIG initiation' and 'visit':

- Number of motor symptoms
- Number of motor symptoms in appropriate categories
- Bradykinesia (yes, no, unknown)
  - If yes: Severity

Frequency

- Rigidity (yes, no, unknown)
  - o If yes: Severity

Frequency

- Tremor (yes, no, unknown)
  - o If yes: Severity

Frequency

- Dystonia / cramps (yes, no, unknown)
  - o If yes: Severity

Frequency

- Gait Impairment (except freezing of gait (FOG); yes, no, unknown)
  - If yes: Severity

Frequency

- Balance problems (yes, no, unknown)
  - o If yes: Severity

Frequency

- Hypophonia (yes, no, unknown)
  - o If yes: Severity

Frequency

- Dysphagia (yes, no, unknown)
  - o If yes: Severity

Frequency

- Nocturnal/morning akinesia (yes, no, unknown)
  - If yes: Severity

Frequency

- Freezing of gait (FOG; yes, no, unknown)
  - If yes: Severity

Frequency

- Other (yes, no)
  - If yes: List of symptoms

#### Non-motor symptoms

Separately for 'immediately prior to LCIG initiation' and 'visit':

- Number of non-motor symptoms
- Number of non-motor symptoms in appropriate categories
- Anxiety (yes, no, unknown)
  - o If yes: Severity

Frequency

- Pain (yes, no, unknown)
  - If yes: Severity

Frequency

- Cognitive Impairment (yes, no, unknown)
  - If yes: Severity

Frequency

- Depression (yes, no, unknown)
  - o If yes: Severity

Frequency

- Apathy (yes, no, unknown)
  - o If yes: Severity

Frequency

- Fatigue (yes, no, unknown)
  - If yes: Severity

Frequency

- Urinary symptoms (yes, no, unknown)
  - If yes: Severity

Frequency

- Constipation (yes, no, unknown)
  - o If yes: Severity

Frequency

- Orthostatic hypotension (yes, no, unknown)
  - If yes: Severity

Frequency

- Other (yes, no)
  - o If yes: List of symptoms

#### Symptoms related to treatment

Separately for 'immediately prior to LCIG initiation' and 'visit':

- Number of symptoms related to treatment
- Number of symptoms related to treatment in appropriate categories
- Hypersexuality (yes, no, unknown)
  - o If yes: Severity

Frequency

- Compulsive shopping (yes, no, unknown)
  - o If yes: Severity

Frequency

- Gambling (yes, no, unknown)
  - If yes: Severity

Frequency

- Binge Eating (yes, no, unknown)
  - If yes: Severity

Frequency

- Punding (yes, no, unknown)
  - o If yes: Severity

Frequency

- Dopamine Dysregulation syndrome (yes, no, unknown)
  - If yes: Severity

Frequency

Other (yes, no)

 Total number of symptoms calculated as sum of the number of motor symptoms, number of non-motor symptoms and number of symptoms related to treatment

#### Co-morbidities

Separately for 'immediately prior to LCIG initiation' and 'visit':

- Any major co-morbidity (yes, no)
- Co-morbidities (multiple answers)
- For each co-morbidity:
  - o If ticked: relation to PD (yes, no)
  - Additionally if 'Cognitive dysfunction' ticked: Severity
- If 'Other' co-morbidity ticked: Specification (MedDRA coded)

#### Historical therapy discontinued prior to considering LCIG initiation

- Any device aided therapy other than LCIG in the past (yes, no)
  - If yes: Therapy (multiple answers)

Separately for DBS and Apomorphine:

- Duration: over all entries the treatment duration (end date minus start date +1) will be summarized
- Reason for discontinuation (multiple answers)
- Any dopamine agonists in the past (yes, no)
  - o If yes: Therapy (multiple answers, patient based)

Separately for each therapy:

- Duration: over all entries the treatment duration (end date minus start date +1) will be summarized
- Reason for discontinuation (multiple answers)

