Interim outcomes of the GREENFIELD observational study on 145 patients with APD in Italy compared clinical data before and during LCIG therapy. Initiation of LCIG led to significant clinical improvement and the intake of add-on PD medication was largely reduced: for instance, oral levodopa use decreased from 96.9% before LCIG start to 5% (during the day) and 26% (at night); use of dopamine agonists decreased from 64.1% to 30%. However, thus far, results are only derived from a mean treatment period of 14 months, and date are still incomplete [9].

Rationale

LCIG (Duodopa®) appears to possess the potential to be used as monotherapy in many patients, or at least enable significant reductions of the add-on PD medication. Thereby, LCIG may achieve a much-needed simplification of the treatment regimen, allowing for a reduction of detrimental drug-drug interactions [6].

So far, data on patients in whom LCIG monotherapy or significant reductions of add-on PD medication was achieved, have been derived from two clinical studies with rigorous protocols [7, 8], and therefore cannot be easily translated into routine clinical practice. Also, recent observational studies demonstrated overall varying approaches in the management of add-on PD medications in routine clinical practice before and after initiation of LCIG treatment [9, 10].

For APD patients under LCIG treatment there is an opportunity to substantially reduce the need for other add-on PD medication and/or completely discontinue them. This is the primary hypothesis that generates this study.

In summary, no systematic, comprehensive and homogeneous real-world data are available – neither on LCIG monotherapy or LCIG in combination with add-on PD medication, nor on the management (reasons for use and time course) of add-on PD medications before or upon LCIG initiation, or during long-term LCIG maintenance therapy.

The present study attempts to fill this knowledge gap and generate relevant data from routine clinical practice on the usability of LCIG as a monotherapy and in combination with add-on PD medications. In addition, useful data on the handling of add-on PD medication (e.g., tapering, introduction), upon LCIG initiation and over long-term use shall be collected.

Research Question and Objectives 8.0

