#### 6.4 Primary variable

There are two primary variables:

1. LCIG monotherapy 1 (yes, no) at LCIG initiation and at 3, 6, 9, and 12 months after LCIG initiation

with the following definition:

- LCIG monotherapy means that the patient is not on any add-on PD medication or PD therapy at the respective time point.
- 2. LCIG monotherapy 2 (yes, no) at LCIG initiation and at 3, 6, 9, and 12 months after LCIG initiation

with the following definition:

LCIG monotherapy means that the patient is allowed to take an add-on PD medication or PD therapy at the respective time point, however, only in the evening after the LCIG infusion is completed (i.e. reason for start of add-on PD medication: other).

Additional specifications for both variables are:

- Medications for indications secondary to PD are allowed.
- If the reason for add-on PD medication is missing the medication will be considered as taken during LCIG infusion (i.e. no monotherapy).
- LCIG initiation date is the start date of the first LCIG infusion.
- 3 months after LCIG initiation is calculated as LCIG initiation date + rounded (3 [months] x 30.4 [days]). 6, 9, and 12 months after LCIG initiation will be calculated analogously.
- For LCIG initiation date with missing day the 15th will be used.

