#### 7.8 Regression analyses

For the application of regression analysis, missing/unknown data for prognostic factors are imputed. Imputation is planned to be accomplished by a regression based single imputation method where missing values of one predictor variable are predicted by regression models with a set of remaining potential prognostic variables as independent variables. This might require adequate preprocessing of the data. Modification of this imputation strategy is possible if implied by the data.

Regression analyses will be evaluated for FAS and conducted on imputed data.

Regression analyses will be performed separately for each of the two primary variables (see Section 6.4):

LCIG monotherapy 1 (LCIG monotherapy 2, respectively) at 12 months after LCIG initiation will be used as dependent (i.e. response) variable in two multivariable logistic regression models. The independent variables (i.e. potential predictors) will be checked for collinearity.

For the first multivariable logistic regression model the following variables will be considered as potential predictors (i.e. independent variables):

Table 7-2: Potential predictors used for regression analysis 1

Variable	Range	Dichotomization/Grouping
Age	numeric	-
Gender	Male, Female	Male vs. Female
Race	White, Black, Asian, Mixed, Other	White vs. Non-White
Education	No formal education, primary school, secondary school, non-university professional education, university	Less than secondary school vs. secondary school or higher
Total number of symptoms	numeric	
Number of symptoms related to treatment	numeric	
Number of motor symptoms	numeric	-
Number of non-motor symptoms	numeric	-
Total daily LEDD at LCIG initiation	numeric	-
Time from PD diagnosis to start of LCIG	numeric	-
Duration of 'Off' state time during a 24h period	numeric	-
Duration of dyskinesia during a 24h period	numeric	-
UPDRS V prior to LCIG initiation (if available)	numeric	-
Any device aided therapy other than LCIG in the past	Yes, No	Yes vs. No
Any dopamine agonists in the past	Yes, No	Yes vs. No
PD motor phenotype	Tremoric, Akinetic rigid, Mix	
Time from PD diagnosis to motor fluctuation	numeric	
Time from PD diagnosis to onset of morning akinesia	numeric	
Country		
GNI	numeric	

Categorical predictors will be dichotomized / grouped as shown in Table 7-2 in order to simplify interpretation.

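### Table 7-2 codes patients whose only dopamine agonist or device therapy is still ongoing at LCIG start as 'No' together with never-users, so the history coefficients can differ from null when past use has no effect

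*SAP*

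**What the plan says.** SAP 6.3 has a block headed "Historical therapy discontinued prior to considering LCIG initiation". It contains two yes/no items, one for device-aided therapy other than LCIG and one for dopamine agonists. The details under a 'yes' fit stopped therapy only: duration from start date to end date, and reason for discontinuation.

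SAP 7.8, Table 7-2, carries both items into the first regression model as "Any dopamine agonists in the past" and "Any device aided therapy other than LCIG in the past", each contrasted Yes vs. No. The SAP gives no other definition of either. The response is monotherapy 1 or, in a separate model, monotherapy 2; its value "at 12 months after LCIG initiation will be used as dependent" variable. Predictors are selected by backward elimination at 0.05.

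SAP 6.4 defines monotherapy 1 strictly: "LCIG monotherapy means that the patient is not on any add-on PD medication or PD therapy at the respective time point". Monotherapy 2 permits an add-on taken only after the day's infusion has ended. SAP 6.5 lists dopamine agonists, apomorphine and deep brain stimulation (DBS) among the add-on categories.

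**The concern.** Under the SAP 6.3 heading, 'Yes' means that an agonist was stopped before LCIG was considered. 'No' covers two unlike groups: patients who never took an agonist, and patients whose only agonist is still running when LCIG starts. The second group has a drug left to withdraw before monotherapy 1 is possible; never-users and past users do not. Pooling the two changes the monotherapy rate in the reference group for a reason unrelated to treatment history. Ongoing DBS or apomorphine infusion with no earlier stopped device raises the same problem for the device item.

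Nothing else in Table 7-2 marks ongoing use. "Total daily LEDD at LCIG initiation" sums over all drugs, so it reflects an ongoing agonist only indirectly, and Table 7-1 has no conversion factor for DBS. A collinearity check does not detect a mixed reference group.

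Identifying patient-profile predictors of monotherapy is a stated secondary objective. At stake is a reported odds ratio for 'past agonist use' that reflects how patients were distributed at LCIG start and says little about history.

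**Working it through.** **The plan's own figure.** The plan gives no figure for this predictor. Its one computed figure reproduces: N = 1.96² × 0.5 × 0.5 / 0.05² = 384.15, rounded up to 385 evaluable patients (Protocol 9.5). N = 385 is used below.

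**Inputs from the documents**
- Agonist use before LCIG 64.1%, during LCIG 30% (Italian observational study, Protocol 7.0).
- Monotherapy m = 36–40% (multinational registry, Protocol 7.0). That figure excludes oral add-ons only, so it approximates monotherapy 1.

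**Assumptions, not in the documents**
- s = share of patients off agonists at LCIG start who had stopped one earlier: 25%, 50%, 75%.
- t = share of current users who had earlier stopped a different agonist and are therefore 'Yes': 0 to 75%.
- All users during LCIG were already users at LCIG start.
- Past use has no effect: true odds ratio 1 for stopped vs. never.

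**Null model for monotherapy 1**
1. Share of current users who stay on the agonist: 30 / 64.1 = 46.8%. They fail monotherapy 1 by definition.
2. Everyone else has probability q = m / 0.70. At m = 38%, q = 54.3%.
3. Monotherapy rate in current users: 54.3% × (1 − 0.468) = 28.9%. Check: 0.641 × 28.9% + 0.359 × 54.3% = 38%.
4. Example with s = 50%, t = 0:
   - 'Yes' share = 0.359 × 0.5 = 0.1795, about 69 patients, rate 54.3%.
   - 'No' rate = (0.38 − 0.1795 × 0.543) / 0.8205 = 34.4%, about 316 patients.
   - Odds ratio = (0.543 / 0.457) / (0.344 / 0.656) = 2.26.
5. Example with s = 50%, t = 25%:
   - 'Yes' share = 0.1795 + 0.641 × 0.25 = 0.340, rate 42.3%.
   - 'No' rate 35.8%. Odds ratio 1.32.

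**Crude odds ratio when the true value is 1**

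| t | Range over s = 25–75%, m = 36–40% | At s = 50%, m = 38% | Chance of p < 0.05 at s = 50%, m = 38% |
|---|---|---|---|
| 0 | 2.01–2.63 | 2.26 | 86% |
| 10% | 1.31–2.10 | 1.69 | 59% |
| 25% | 1.00–1.69 | 1.32 | 24% |
| 50% | 0.77–1.31 | 1.00 | nominal |
| 75% | 0.59–1.00 | 0.76 | 24% (wrong direction) |

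The bias is nil when t = s and reverses when t > s.

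**Does adjustment for LEDD repair it?** Logistic regressions were simulated (1,500 per scenario) at m = 38% and s = 50%. Assumed values were a mean non-agonist LEDD of 800 mg (SD 200 or 400) and a mean agonist LEDD of 250 mg.
- At t = 0 the LEDD-adjusted odds ratio was 1.98–2.18, against 2.26 crude, and significant in 69–81% of runs.
- At t = 25% it was 1.24–1.30, against 1.32 crude, and significant in 14–23% of runs.
- With an added term for agonist use at LCIG start, at t = 0, the odds ratio for past use was 0.98–1.01 and significant in 4.4–6.3% of runs, close to nominal.

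**The case against.** The strongest case on the other side has five parts.

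- **Not every current user is 'No'.** A reader might infer that all patients on an agonist at LCIG start fall in the reference group. The documents do not support that. SAP 6.3 records agonists per therapy with multiple answers, so a current user who earlier stopped a different agonist is 'Yes'. This stands, and it is why neither size nor direction is fixed.
- **Survival in the model is not assured.** A reader might infer that a spurious benefit will pass elimination at 0.05. It could. At t = 25% in the central case the crude chance is 24%, and the full model has many other predictors. This also stands.
- **The device item has no number behind it.** The 64.1% concerns agonists only. If most patients never had a device, 'No' there mostly means never used and the dilution is small. This stands as to size; the coding problem is the same in kind.
- **The coding is read from a heading.** The data form is not in the documents, so how sites answer for a running agonist cannot be checked. The end-date and discontinuation items nevertheless support the reading.
- **Stopping an agonist before LCIG is a legitimate patient characteristic, and SAP 7.10 calls the study exploratory.** True, but the Table 7-2 label drops the restriction to stopped therapy, and a mixed reference group is hard to interpret even in exploratory work.

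**Conclusion.** The concern holds as a defect in how two predictors are coded. As written, their coefficients can depart from 1 when past use has no effect, and the plan contains no variable that separates ongoing from never use.

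For the agonist item and monotherapy 1, the spurious odds ratio is about 2.0–2.6 at t = 0, 1.3–2.1 at t = 10% and 1.0–1.7 at t = 25%. Over the t range examined it falls as low as 0.59. These figures rest on usage and monotherapy rates from other studies that the protocol cites, and on s and t, which are assumed. It would be wrong to conclude that the model must show a benefit of past use.

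Under monotherapy 2, an agonist taken only after the infusion does not count against the patient, so the bias should be smaller; it was not quantified. No size can be given for the device item. The primary percentages are unaffected. The change should be made because a secondary objective could otherwise be misreported.

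**What to change.** In Table 7-2, replace the agonist item with three levels: never used, stopped before LCIG, and ongoing at LCIG initiation. 'Ongoing' should take precedence for a patient who stopped one agonist and is still on another. Alternatively, keep the 'stopped' item and add an indicator for an agonist ongoing at LCIG initiation. Report the history effect as stopped vs. never, separately from the contrast for ongoing use. Apply the same coding to device therapy where cell counts allow.

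No new data are needed. Protocol 9.2.7.5 collects PD medication right before LCIG with dates, and SAP 6.5 records add-on agonists and DBS at LCIG initiation. The cost is a wording change in the SAP, one recode and one extra degree of freedom per variable. The never-user group may be small, which would make the stopped vs. never contrast imprecise.

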# Separate lists of other medications and therapies only for indications secondary to PD will be provided for:

- before LCIG initiation
- after LCIG initiation
- at LCIG initiation
- at 12 months after LCIG initiation
- · at study visit

#### Patient reported outcomes (PROs)

• PDQ-8: Eight single items

PDQ-8 summary index

QUIP-RS: Compulsive gambling

Sexual behavior

Buying Eating

Hobbyism-Punding PD medication Total ICD scores Total QUIP-RS score PDSS-2: Motor symptoms at night

PD symptoms at night

Disturbed sleep Total PDSS-2 score

BMQ: General-Overuse

General-Harm Specific-Necessity Specific-Concern

## Questionnaires reported by physicians

UPDRS (separately for 'prior to LCIG initiation' and 'patient visit if available'):

Part I

Part II

Part III

Part IV

- o Dyskinesias and Dystonia
- Motor fluctuations
- Other complications
- Depending on data quality: Dyskinesias duration during waking day in hours (from item 32)
- Dyskinesias duration during waking day in categories (item 32)
- Severity of dyskinesia (item 33)
- Pain related to dyskinesia (item 34)
- o Early morning dystonia (item 35)
- o 'Off' state time during waking day in hours (from item 39)
- o 'Off' state time during waking day in categories (item 39)

Part V

NMSS: Nine domain scores

Total NMSS score

 Total MMSE score (separately for 'prior to LCIG initiation' and 'patient visit' if available)

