9.2.7.3 Patient Demographics and socio-demographics

The physician will collect patient demographic information and record it on the eCRF. The demographic information includes age, sex, race and ethnicity, and education (where applicable and allowed).

Socio-demographic data to be collected before LCIG initiation and at the patient visit and includes information on living situation, current primary occupation, and the need of a caregiver (and extent of care needed)

9.2.7.4 **Medical History and PD History**

A complete medical history (PD and non-PD) will be obtained and recorded in the eCRF as available from the patient files. Information on PD includes phenotype, date of first PD

diagnosis, year of first occurrence of motor fluctuations, percentage and daily hours spent in off state or spent in on-state with troublesome/non-troublesome dyskinesia, presence of PD symptoms (motor and non-motor), Unified Parkinson's Disease Rating Scale (UPDRS), Modified Hoehn & Yahr stage (UPDRS part V), and PD-related comorbidities.

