9.4.3.7 Mini-Mental State Examination (MMSE)

The MMSE [59] is a brief, 30-point questionnaire, administered by a trained rater, which provides a quantitative measure of cognitive mental status in adults and is widely used to screen for cognitive impairment and to estimate the severity of cognitive impairment at a given point in time, to follow the course of cognitive changes in a patient over time, and

to document response to treatment. In this study, MMSE will be used to evaluate cognition status at cross-sectional visit, and if available to collect it before starting LCIG treatment.

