#### 4.4 Methods of measurement and documentation

Patient data and site characteristics were to be documented on the eDRF. In addition, patients were asked to complete the following questionnaires: Parkinson's Disease Quality of Life Questionnaire (PDQ-8), Questionnaire for Impulsive-Compulsive Disorders in Parkinson's Disease - Rating Scale (QUIP-RS), Parkinson's Disease Sleep Scale-2 (PDSS-2), and Beliefs Medication Questionnaire (18-item BMQ). Physicians should complete the following questionnaires: Unified Parkinson's Disease Rating Scale (UPDRS), Non-Motor Symptoms Scale for Parkinson's Disease (NMSS), Mini-Mental State Examination (MMSE), and Healthcare Resource Utilization Questions (HCRU). Data from questionnaires were also to be recorded on the eDRF.

An overview of activities and procedures is given in Table 4-1.

Table 4-1: Activities and procedures

Activity/Procedure	Before LCIG initiation	LCIG initiation	During LCIG treatment	Patient visit
	Retrospective data from patient files			
Center characteristics	X			3
Physician experience and treatment preference	X			
Patient demographics	X		ė.	
Patient socio-demographics	X			X
Medical History and PD History	X			X
PD medication before starting LCIG	X			
Add-on PD medication since LCIG initiation		X	X	X
Clinical PD status	X	X		
LCIG infusion data		X	X	X
Concomitant Medication (for indications secondary to PD)	X	X	X	X
Behaviour/mentation/mood (UPDRS Part I)	X		2	X
Activities of daily living (UPDRS Part II)	X			X
Motor examination (UPDRS Part III)	X			X
Treatment complications (UPDRS Part IV)	X			X
Disease Stage (Modified Hoehn & Yahr stage, UPDRS Part V)	X			X
Non-motor Symptoms Scale (NMSS)				X
Questionnaire for Impulsive-Compulsive Rating Scale (QUIP-RS)			6	X
Mini-Mental State Examination (MMSE)	X			X
Quality of Life (PDQ-8)			ā	X
Parkinson's disease Sleep Scale Version 2 (PDSS-2)				X
Healthcare Resource Utilization Questions (HCRU)				X
Beliefs Medication (BMQ)				X
Adverse Events / Adverse Reactions / Product complaint		X	X	X

In detail the following information was documented:

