## 7 Statistical methodology

## 7.1 General methodology

All statistical analyses will be carried out by means of the SAS® package (version 9.4).

Quantitative data (e.g. age) will be described by the statistical parameters valid N, missing N, mean, standard deviation (SD), minimum, the 25%-quartile, median, the 75%-quartile, and the maximum.

Qualitative data (e.g. gender) will be presented by means of (absolute and relative) frequency distributions. If applicable, two methods will be followed for calculation of percentages. The first method considers missing data as a separate group, which results in the same sample size for all parameters. The second method of calculation is based on the valid data per parameter, excluding patients with missing values ("valid data analysis"). Accordingly, this results in different sample sizes. In general, description of results within the report refers to the "valid data analysis".

For categorical variables associated with score values, the mean will be calculated as well.

Two-sided 95% confidence intervals will be provided for the primary, and if applicable, the secondary variables defined by proportions.

Statistical methods which differ from the above mentioned methods or require further description will be addressed in the following sections.

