#### 7.4 Patient data

Patient disposition will be evaluated for all patients enrolled.

All other variables will be evaluated for FAS according to the methods described in Section 7.1.

Patient data will be analyzed overall and separately for the following three groups:

- Patients on monotherapy 1 at 12 months after LCIG infusion (see Section 6.4)
- Patients on monotherapy 2 at 12 months after LCIG infusion (see Section 6.4)

Patients not on monotherapy 2 at 12 months after LCIG infusion (see Section 6.4) For duration of 'Off' state (hours) and duration of dyskinesia (hours) the difference will be calculated between the time points 'prior to LCIG initiation' and visit (UPDRS IV: modified items 39 and 32) as value at visit minus value prior to LCIG initiation.

'Other' co-morbidities will be coded using MedDRA. Incidence rates will be calculated with respect to System Organ Class and Preferred Term.

Regarding the 'Historical therapy discontinued prior to considering LCIG initiation' patient based means that a therapy type will only be counted once per patient.

A list of other medications and therapies only for indications secondary to PD will be provided including the following information:

- PatientID
- Name of concomitant medication or therapy
- Indication
- Total daily dose
- Dose unit
- Start date
- End date
- Ongoing at the end of study

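### For UPDRS and MMSE, the means before LCIG and at the visit rest on unequal sets of patients, and the SAP's within-patient difference does not extend to these scores

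*SAP*

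**What the plan says.** **Where the pre-LCIG values come from.** Protocol 9.2.7.4 lists UPDRS and Hoehn & Yahr stage within the medical and PD history, which "will be obtained and recorded in the eCRF as available from the patient files". For the MMSE, Protocol 9.4.3.7 says that "MMSE will be used to evaluate cognition status at cross-sectional visit, and if available to collect it before starting LCIG treatment". SAP Table 4-1 marks UPDRS Parts I–V and MMSE both before LCIG and at the visit, and heads its retrospective columns "Retrospective data from patient files". SAP Table 7-2 also makes pre-LCIG UPDRS V conditional on availability.

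**Where the visit values come from.** The study administers them. Protocol 9.2.7.8 and Table 1 plan UPDRS I–V and MMSE at the visit, and Protocol 9.4.3.1 confirms that all five UPDRS parts are used.

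**How the two times are reported.** SAP 6.3 has "UPDRS (separately for 'prior to LCIG initiation' and 'patient visit if available" and "Total MMSE score (separately for 'prior to LCIG initiation' and 'patient visit' if available". SAP 7.1 describes quantitative data by valid N, missing N, mean, SD and quantiles. SAP 7.4 applies this to the full analysis set, overall and in three groups defined by monotherapy status at 12 months.

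**Where a within-patient difference is planned.** SAP 7.4: "For duration of 'Off' state (hours) and duration of dyskinesia (hours) the difference will be calculated", as visit minus prior, with the visit value taken from modified items 39 and 32 of UPDRS IV. No such difference is given for the UPDRS part scores, the Part IV sub-scores or the MMSE.

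**The concern.** A table with a pre-LCIG mean beside a visit mean invites a before/after reading. Here the first mean uses only patients whose file holds a score, and the second uses, by plan, everyone. A chart is more likely to hold a formal UPDRS or MMSE at some sites than at others, and perhaps when cognitive decline was suspected, so the charted patients need not be typical. This is a plausible inference; the documents do not state it.

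If they are not typical, the gap between the two means is part change and part difference between patients. The same tables are shown by monotherapy group, so unequal charting between groups could look like a difference in clinical course. Nothing else in the SAP repairs this. Section 6.7 deals only with missing single items, and the imputation in Section 7.8 is confined to regression predictors.

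**Working it through.** **The plan's own figure.** The documents give no figure on this point. Their one calculated number is the sample size, 1.96² × 0.5 × 0.5 / 0.05² = 384.2, rounded up to 385. It reproduces, but nothing below depends on it.

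**Which patients each summary uses.**

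| Summary | Patients contributing |
|---|---|
| Pre-LCIG UPDRS or MMSE | those with a score in the file |
| Visit UPDRS or MMSE | planned for all |
| Visit minus prior, OFF and dyskinesia hours | those with both values |
| Visit minus prior, UPDRS I–V, Part IV sub-scores, MMSE | not planned |

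**Size of the mismatch.** Let a be the share with a pre-LCIG value. Let P1 and V1 be the pre-LCIG and visit means in those patients, and V0 the visit mean in the rest. Assume everyone has a visit value. Then:

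- visit mean in all = a × V1 + (1 − a) × V0
- difference of the two reported means = a × V1 + (1 − a) × V0 − P1 = (V1 − P1) + (1 − a) × (V0 − V1)

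The first term is the paired change in patients with a baseline. The second is the error, (1 − a) × d with d = V0 − V1. It takes the sign of d, so it can exaggerate or hide a change.

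**Illustration.** Both a and d are assumptions.

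| a | d = 3 points | d = 6 points |
|---|---|---|
| 0.3 | 0.7 × 3 = 2.1 | 0.7 × 6 = 4.2 |
| 0.5 | 0.5 × 3 = 1.5 | 0.5 × 6 = 3.0 |
| 0.7 | 0.3 × 3 = 0.9 | 0.3 × 6 = 1.8 |

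In SD units, a gap of 0.2 to 0.5 SD gives an error of 0.14–0.35 SD at a = 0.3, 0.10–0.25 at 0.5, 0.06–0.15 at 0.7 and 0.02–0.05 at 0.9. At a = 1 or d = 0 it is zero.

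**Between groups.** If 70% of one monotherapy group and 30% of another had a baseline, with the same true change and the same d in both, the apparent changes would differ by 2.1 − 0.9 = 1.2 points (d = 3) or 4.2 − 1.8 = 2.4 points (d = 6).

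**Precision of a paired analysis.** With about 400 patients, a = 0.3 gives 120 pairs and a = 0.7 gives 280. With equal SDs and correlation r between the two times, the standard error of the paired mean is √(2(1 − r)/n) SD. For r between 0.7 and 0.3 (assumed), this is 0.071 to 0.108 SD at 120 pairs and 0.046 to 0.071 SD at 280.

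**The case against.** The best defence is that nobody asked for change in these scores. No primary or secondary objective, and no SAP primary or secondary variable, concerns change in UPDRS or MMSE. The protocol presents them mainly as current status at the visit, and the SAP never calls the separate means a change. Valid N and missing N are printed at each time, so the mismatch is visible. All of this stands, and it limits the weight of the point. It does not remove it, because the paired mean and its SD cannot be recovered from two marginal summaries, and the SAP itself uses within-patient differences for OFF and dyskinesia hours and for LCIG dose.

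A reader might infer more than the documents support:

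- *That the SAP plans no paired change at all.* SAP 7.4 plans one for OFF and dyskinesia hours, both of which appear in the UPDRS list of SAP 6.3.
- *That the two times describe different patients.* Those with a pre-LCIG value are, by plan, largely a subset of those with a visit value. Coverage of all patients is itself only the plan: SAP 4.4.5 drops a Part IV sub-score when any item is missing.
- *That the protocol foresees no UPDRS I–IV before LCIG.* Table 1 marks these rows only at the visit, but Protocol 9.2.7.4 puts UPDRS in the PD history, and that row is marked before LCIG.
- *That the SAP 7.1 sentence beginning "In general, description of results within the report refers to the" governs these means.* It belongs to the paragraph on percentages for qualitative data, so it reaches only the categorical items. For the scores, the relevant rule is valid N and missing N.

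**Conclusion.** The point holds for UPDRS Parts I–V, the Part IV sub-scores and the MMSE. As planned, any before/after comparison of their means carries an error of (1 − a) × d. Under the assumed ranges that is 0.9 to 4.2 UPDRS III points. Neither a nor d is in the documents, and the true error may be near zero. That charted patients are a selected group is plausible but not shown. The consequence is confined to descriptive tables, overall and by monotherapy group, and to any text drawn from them. No primary or secondary result depends on it.

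The change is still worth making, because it applies the SAP's own method to data that are already being collected.

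**What to change.** - In SAP 7.4, extend the visit-minus-prior difference to UPDRS Parts I–V, the Part IV sub-scores and MMSE. Compute it in patients with both values, and report the number of pairs, mean, SD and 95% confidence interval, overall and for the three monotherapy groups.
- Show visit values separately for patients with and without a pre-LCIG value. This gives a direct look at d.
- Base any before/after statement on the paired result.
- In SAP 6.3, the UPDRS line as printed attaches the words *if available* to the visit, probably through a misplaced quotation mark. Move them so that they qualify the pre-LCIG value, and word the MMSE line the same way.

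The cost is a few lines of SAP text and a few tables, with no new data. The paired result will rest on fewer patients and will describe only those with a charted baseline, so it removes the mixing of patients but not the possible selection. The report should say so.
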